6.2.1 Ribociclib

Ribociclib is an investigational agent for the treatment of patients with hormone receptor positive metastatic breast cancer. It does not require specific prophylactic or supportive regimens as per the Investigator Brochure (IB) and based on the precedent set in ongoing clinical trials. It is an oral therapy and can be administered with or without food according to the IB. The planned dose will be 600 mg oral daily (3 x 200 mg capsules/tablets), with dose adjustments only as specified in Section 7.

6.2.2 Fulvestrant

Fulvestrant is FDA-approved for the treatment of metastatic hormone receptor positive breast cancer. It does not require specific prophylactic or supportive regimens. It is an intramuscular therapy that should be prepared according to manufacturer's recommendations. It can be administered with or without food.

6.2.3. Exemestane

Exemestane is FDA-approved for the treatment of metastatic hormone receptor positive breast cancer. It does not require specific prophylactic or supportive regimens. It can be administered with or without food.

6.2.4 Treatment Duration:

Patients will receive trial treatment until disease progression, unacceptable toxicity, or death or withdrawal from study based on patient choice or treating physician's discretion. Every effort will be made to follow patients for primary and secondary outcomes regardless of treatment discontinuation for any reason. Crossover is not built into the study.

Patients may voluntarily discontinue from the study treatment for any reason at any time. If a patient decides to discontinue from the study treatment, the investigator must make every effort (e.g. telephone, e-mail, letter) to determine the primary reason for this decision and record this information in the patient's chart and on the appropriate CRF pages. They may be considered withdrawn if they state an intention to withdraw, fail to return for visits, or become lost to follow-up for any other reason.

The investigator should discontinue study treatment for a given patient if, on balance, he/she believes that continuation would be detrimental to the patient's well-being. Patients may voluntarily withdraw from the study or be dropped from it at the discretion of the investigator at any time.

Premature patient withdrawal refers to the point/time when the patient exits from the study prior to the planned completion of all study treatment administration and/or assessments; at this time, all study treatment is discontinued and no further assessments are planned, unless the patient will be followed for progression and/or survival.

Patients may be withdrawn from the study treatment if any of the following occur:

- Adverse Event (Documented episode of ventricular tachycardia, or ventricular fibrillation; Complete heart block (Grade III AV block) or Second degree AV block Mobitz type II)
- Lost to follow-up
- Physician decision
- Progressive Disease
- Study terminated

Patients must be withdrawn from the study treatment if any of the following occur:

- Pregnancy
- Death
- Subject/Guardian decision

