6.4 Duration of Therapy

In the case of registration scenario #1, patients will continue on CDK4/6 inhibitor and aromatase inhibitor therapy until disease progression*. At that time, patients will be randomized to receive fulvestrant (or exemestane) +/- continuation of CDK4/6 inhibition with ribociclib. In the case of registration scenario #2, patients will be randomized immediately to receive fulvestrant (or exemestane) +/- continuation of CDK4/6 inhibition with ribociclib.

After randomization, in the absence of treatment delays due to adverse event(s), treatment may continue until

one of the following criteria applies:

- Disease progression
- Inter-current illness that prevents further administration of treatment
- Unacceptable adverse event(s)
- Patient decides to withdraw from the study
- General or specific changes in the patient's condition render the patient unacceptable for further treatment in the judgment of the investigator. **OR**
- Pregnancy
- Removal by Sponsor (e.g., unblinding by Sponsor-Investigator).

In the absence of one of the events listed above, there is no pre-defined limit on the number of potential cycles.

* In the case of registration scenario # 1, some patients may discontinue treatment in the pre-randomization phase due to events other than disease progression, including those listed above. (i.e. unacceptable toxicity, patient decides to withdraw from the study, etc.). Those patients will come off study prior to randomization and will not be evaluable for the primary outcome.

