6.6 Criteria for Removal

Patients will be removed from study when any of the criteria listed in Section 6.4 applies. The reason for study removal and the date the patient was removed must be documented in source documentation and the Case Report Form. Patients continuing study treatment following unblinding by the Sponsor-Investigator will be treated as per standard of care and therefore will no longer be required to follow the study calendar or complete any of the study assessments that are not part of standard of care. Following unblinding by the Sponsor-Investigator, study teams will no longer be required to enter data into the database aside from SAEs and patient status updates (in the Screening/Enrollment tab in Velos).

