		^A Exceptions to the +/- 4 days are CT C/A/P + bone scan (OR PET) which should be performed within 28 days of trial registration and after every third cycle of treatment (within 14 days of day 1 of each third cycle – ideally within 7 days of day 1) and tissue biopsy (+/- 7 days).						
		^B Every 4 weeks. Day 1 visits for each cycle should occur at 28±4 days from day 1 of the previous cycle. Blood draws on that day should also fall within this +/- 4 day window. Exceptions to the +/- 4 days are CT C/A/P + bone scan (OR PET) as described above. The +/- 4 day window includes C1D15.						
		^C Ribociclib (or placebo) will be supplied per study. On D1 of every cycle prior to drug dispensation and dose administration, subject's disease status/non-progression will be confirmed by the treating investigator, including clinical and radiographic assessment. RECIST restaging will be confirmed for the most recent scans received, including documentation of investigator sign off on calculation of percentage change from baseline and nadir and overall response, prior to treatment. If the new scan information becomes available mid cycle, the study team will inform the subject if treatment discontinuation is required per protocol in real time, and document date of treatment discontinuation.						
		^D Serum Pregnancy test (women of childbearing potential)						
		^E Albumin, alkaline phosphatase, total bilirubin, bicarbonate, BUN, calcium, chloride, creatinine, glucose, potassium, total protein, SGOT [AST], SGPT [ALT], sodium.						
		^F EKG will be performed at baseline, C1D15, C2, and Cycle 4. If grade 3 or 4 QTC prolongation occurs, see section 7.3 for monitoring/dose modification. If no EKG abnormalities, additional EKGs are not required for cycles after C4a or C4b, except						

		Progression.
		^G Scans should be performed within 28 days of study registration, prior to every third cycle of treatment (i.e, preferably within 7 days of Cycle 4a day 1, Cycle 7a day 1, Cycle 10a day 1, and so on, but allowance for up to within 14 days of the next treatment cycle). Corresponding RECIST restaging will be conducted in real time following scans and signed (electronically or wet ink) by the investigator, including confirmation of overall disease status per RECIST v.1.1.1.

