The table below applies to Scenario 2 patients who were Actively receiving treatment when unblinded by the Sponsor-Investigator at the end of August 2023, due to the expiration and discontinuation of the Novartis manufactured placebo for this study. Guidance was provided to all study sites noting that all patients that are Active/On Treatment on scenario 2 will undergo an unblinding process following which patients will continue to receive the assigned treatment: patient who received Ribociclib will continue to do so and patients who received Placebo will continue to receive the endocrine treatment alone, as part of the study. Please note, the study does not allow for crossover between the study groups.

	Patient Visit ¹ (ongoing)
SAE ²	X
Disease Progression ³	X
Patient Status on Study ⁴	X

1. Visit frequency should be determined as per standard of care.
2. All SAEs experienced by patients receiving study treatment should be reported as per section 8.2.7 and entered in the Velos database.
3. Disease Progression should be documented in the patient statuses in velos, as reason for removal from study treatment, if applicable.
4. Any update to the patients' stua y status should be entered in Velos.

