11.2.3 Disease Parameters

Patients with both measurable and un-measurable disease will be enrolled in the study. Treatment will continue until disease progression as defined above or unacceptable toxicity develops as determined by the treating physician.

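### Section 6.2.4 makes stopping optional after four named cardiac events that 7.3 does not cover by name, and lists progression the same way against 6.4, 6.6 and 11.2.3

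*Combined protocol and SAP*

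**What the plan says.** Section 6.2.4 (Treatment Duration) opens with "Patients will receive trial treatment until disease progression, unacceptable toxicity, or death". It then gives two lists. The first, headed "Patients may be withdrawn from the study treatment if any of the following occur", contains progressive disease and, as its only named adverse events, documented ventricular tachycardia or fibrillation, complete heart block and second-degree Mobitz II block. It also contains loss to follow-up, physician decision and study termination. The second list uses *must* and contains only pregnancy, death and the decision of the subject or guardian.

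Elsewhere the protocol treats progression as an end point for treatment:

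- 6.4: "After randomization, in the absence of treatment delays due to adverse event(s), treatment may continue until" one of a set of criteria applies, and disease progression is the first.
- 6.6: "Patients will be removed from study when any of the criteria listed in Section 6.4 applies".
- 11.2.3: "Treatment will continue until disease progression as defined above or unacceptable toxicity develops as determined by the treating physician".
- Study calendar notes (10.1 and 10.2): before drug is dispensed on Day 1 of each cycle, "disease status/non-progression will be confirmed by the treating investigator, including clinical and radiographic assessment".

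Section 7.3 has dose-modification tables for hematologic and hepatic toxicity, QTc prolongation and ILD/pneumonitis, and a general table for other adverse reactions. No row is specific to ventricular arrhythmia or AV block; serious arrhythmia appears only as part of the QTc Grade 4 criterion.

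**The concern.** When a *may* list stands next to a *must* list, a site will reasonably read everything on the first as optional. For progression, that reading contradicts four other statements in the protocol.

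For the cardiac events the wording matters more. Physician decision is already on the optional list, so naming four serious arrhythmias there adds nothing unless it was meant as a specific stopping rule. As written, it is not one. Ribociclib has a known QT effect: Section 8.1 reports two patients at 600 mg, the trial dose, with QTc above 500 ms. Exclusion 10 keeps out patients with clinically significant arrhythmias such as ventricular tachycardia, and with high-grade AV block including Mobitz II and third degree. What is at stake is the safety of an individual patient who has such an event on treatment and is restarted with no named rule against it.

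**Working it through.** The plan gives no figure on this point, so the check is a comparison of texts.

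**Progression.** The optional list in 6.2.4 stands against the opening sentence of the same section, 6.4, 6.6 and 11.2.3. Section 6.6 is the strongest of these, because it makes removal mandatory whenever a 6.4 criterion applies. All four end treatment at progression; only the list makes it optional. For patients on the calendar, the Day 1 check is a further safeguard before each dispensing.

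**Cardiac events.** Section 6.2.1 allows ribociclib dose adjustments only as Section 7 specifies, so 7.3 is where a stopping rule would have to be. Reading its tables for one of the four named events gives:

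| Situation | Table in 7.3 | Result for ribociclib/placebo |
|---|---|---|
| QTc at least 501 ms, or a rise above 60 ms, with signs of serious arrhythmia | QTc, Grade 4 | Discontinue |
| Event graded 4 | Other adverse reactions | Discontinue |
| Event graded 3, QTc Grade 4 criterion not met | Other adverse reactions | Interrupt until Grade 1 or less, restart one level lower; on Grade 3 recurrence, restart lower again at investigator discretion |
| Event graded 2, criterion not met | Other adverse reactions | Interrupt until Grade 1 or less, restart at the same dose; on Grade 2 recurrence, restart one level lower |
| Event graded 1, criterion not met | Other adverse reactions | No dose change recommended |

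The dose levels are 600, 400 and 200 mg. From the starting dose, the Grade 3 row therefore permits two restarts: 400 mg, then 200 mg.

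By comparison, the QTc Grade 3 row requires discontinuation when a QTc above 501 ms recurs, even with no arrhythmia. A recurrent Grade 3 arrhythmia outside the QTc criterion is thus handled more leniently than a recurrent ECG interval.

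Two general clauses remain. Section 6.2.4 says the investigator should stop if continuing would harm the patient, and 6.4 with 6.6 requires removal for an unacceptable adverse event. Both rest on judgement and neither names these events.

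**What cannot be settled.** Whether each of the four events can be graded below 4 depends on CTCAE version 4.0 definitions, which the documents do not reproduce.

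**The case against.** The best answer on progression is that the optional list is a catalogue of withdrawal reasons. It also holds loss to follow-up and study termination, which nobody would call discretionary. The operative rules all point the same way, so no site should treat past progression. That largely stands, and it is why this half is a contradiction in wording and little more. Section 6.3 might also explain the *may*, since it contemplates CNS-limited progression in patients otherwise benefiting. But 6.2.4 is not confined to that case, and the same paragraph of 6.3 says RECIST 1.1 progression must be ruled out.

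A reader might infer that patients continuing after the August 2023 unblinding have no rule requiring them to stop, because under 6.6 they "will no longer be required to follow the study calendar" and note 3 of Table 10.3 reads "Disease Progression should be documented in the patient statuses in velos, as reason for removal from study treatment, if applicable". The documents do not support this. Section 6.6 releases them from the calendar, from assessments outside standard care and from most data entry, but not from 6.4. Its removal rule still applies, and Table 10.3 keeps progression as an item at every ongoing visit. The closing words of note 3 are most naturally read as applying when progression is the reason for removal.

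On the cardiac half, the defence is that Section 8.2.8 describes Grade 4 as covering life-threatening events, that Grade 4 already requires discontinuation, and that 7.3 deliberately leaves room for clinical judgement on individual benefit and risk. This narrows the gap without closing it: an event graded 3 or lower outside the QTc criterion still has a written route to restart. A reader might go further and infer that ventricular fibrillation or complete heart block could be graded 3 and restarted; the documents do not show that. Nor would a restarted patient necessarily be in a state that barred entry. Exclusion 10 concerns clinically significant, uncontrolled disease, whereas restart requires recovery to Grade 1 or less.

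**Conclusion.** The point holds as a minor one. The progression entry contradicts the rest of the protocol but changes little, because 6.4 and 6.6 require stopping for all patients. The cardiac entries leave a real but narrow gap: for the four named events, stopping is optional in 6.2.4, and 7.3 requires it only at Grade 4 or when the QTc Grade 4 criterion is met. This rests on at least one of the four being gradable below 4 under CTCAE, which cannot be checked here.

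The number of patients affected should be very small, since Section 8.1 reports no related cardiac abnormality with single-agent ribociclib beyond QTc prolongation and one first-degree AV block. A reader might turn that into a ceiling: zero events in 132 phase I patients gives a 95% upper limit of 1 − 0.05^(1/132) = 2.24%, and 66 × 0.0224 = 1.48 events in the planned ribociclib arm. With all 196 single-agent patients as the base, the limit is 1.52% and the product 1.00. Neither product is a maximum. The calculation treats a confidence limit as a bound and counts only events judged related. It borrows from monotherapy at 50 to 1200 mg and omits the 27 Scenario 1 patients given ribociclib before randomization, so the exposed base lies between 66 and 66 + 27 = 93, depending on overlap. It also does not isolate events graded below 4 and then restarted. No reliable bound can be taken from the documents.

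PFS runs from randomization to progression or death, so its definition, the sample size, alpha and power do not depend on this wording.

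**What to change.** In 6.2.4, move two items to the mandatory list: progressive disease after randomization, and documented ventricular tachycardia, ventricular fibrillation, complete heart block or Mobitz II block. The limit to progression after randomization is needed because, in Scenario 1, progression before randomization leads to randomization. No CNS exception should be written in unless 6.3, 6.4 and 6.6 are first made consistent with it.

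In 7.3, add a row for the four cardiac events requiring permanent discontinuation of ribociclib/placebo whatever the grade. For these events, 6.2.4 should say that the mandatory stop applies to ribociclib/placebo and that endocrine therapy is left to the investigator.

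This is a wording amendment with no new procedures or data. The cost is slightly less investigator discretion to rechallenge after one of these events.

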6.3 General Concomitant Medication and Supportive Care Guidelines

The patient must be told to notify the investigational site about any new medications *he/she* takes after the start of the study treatment. All medications (other than study drugs) and significant non-drug therapies (including vitamins, herbal medicines, physical therapy and blood transfusions) administered within 30 days of study

entry and during the study must be listed on the Concomitant medications/Significant non-drug therapies eCRF.

Fulvestrant, letrozole, and exemestane are FDA approved agents for the treatment of patients with metastatic breast cancer. Per manufacturer Prescribing Information, there are no concurrent supportive or prophylactic regimens recommended for either fulvestrant, exemestane, or letrozole.

Growth Factor Support:

Per manufacturer Investigator Brochure (IB), there are no concurrent supportive or prophylactic regimens recommended for ribociclib. While the rates of grade III/IV neutropenia are considerable with CDK4/6 inhibitors, the rates of febrile neutropenia (FN) are quite low, and well below the 20% threshold for which FN prophylaxis with G-CSF is recommended. Nonetheless, G-CSF is allowed at the treating physician's discretion. Hematopoietic growth factors may be used according to ASCO guidelines.

Radiation Therapy:

If a subject requires additional anti-cancer therapy, the subject must be withdrawn from study treatment, with the exception of palliative radiotherapy (i.e., to bone metastasis or for subjects who have disease progression limited to the CNS but who are otherwise benefiting from study treatment), which may be allowed during the study but must be discussed with the overall principal investigator. Study treatment should be withheld until palliative radiotherapy is terminated. This treatment break should not be considered as treatment interruption. Palliative radiation is permitted if done solely for bone pain relief. It should not be delivered to a target lesion. Cumulative courses of RT should not encompass >25% of irradiated bone marrow. If palliative radiotherapy is initiated after the start of study treatment, the reason for its use must be clearly documented and progression as per RECIST 1.1 must be ruled out.

Given the transient myelosuppressive effects of ribociclib and the long-term myelosuppressive effects of Comp to the axial skeleton in adults, subjects who have received radiation to the spine, pelvis, ribs, or femur should be discussed and approved by the overall principal investigator prior to study re-entry. If anti-cancer treatment follows discontinuation of study treatment due to clinical progression determined by the investigator, the basis for this determination should be documented.

Surgery:

For subjects undergoing minor surgery, it should be scheduled during off week of LEE011/placebo, if possible. LEE011/placebo should preferably be discontinued five days prior to scheduled procedure and should remain on LEE011 hold until appropriate recovery from procedure, per treating physician's discretion.

General medication guidelines:

Medications required to treat adverse events, manage cancer symptoms, treat co-morbid conditions, and supportive care agents, such as analgesics, anti-emetics and anti-diarrhea agents are allowed. Please consult the list of prohibited medications and the list of use with caution medications for further guidance. The patient should notify the investigational site about any new medications taken after the start of the study treatment. All medications administered within 28 days of study entry and during the study period must be listed on the concomitant medications and supplements case report form.

Bisphosphonates / Denosumab:

Bone directed therapy to prevent skeletal related events (SRE's) or to treat osteoporosis with bisphosphonates or denosumab is permitted. While the use of bisphosphonates has been found to reduce the incidence of new bone metastases in patients with metastatic breast cancer, we do not anticipate this to affect

the results of this randomized control trial. Thus, treatment initiated prior to registration or after registration with these agents is permitted. The time of initiation of bone directed therapy should be clearly recorded on the case report forms.

Concomitant therapy requiring caution

Medications to be used with caution during ribociclib in this study are listed below. These medications should be excluded from patient use if possible. If they must be given based on the investigator's judgment, then use with caution and consider a ribociclib interruption if the concomitant medication is only needed for a short time.

- Moderate inhibitors or inducers of CYP3A4/5
- Sensitive substrates of CYP3A4/5 that do not have narrow therapeutic index
- Strong inhibitors of BSEP
- Medications that carry a possible risk for QT prolongation
- Sensitive substrates of the renal transporters, MATE1 and OCT2
- Sensitive substrates of BCR

Prohibited concomitant therapy

The following medications are prohibited during study treatment in the study (see Appendix B, this list is not comprehensive and is only meant to be used as a guide. Please contact the medical monitor with any questions):

- Strong inhibitors or inducers of CYP3A4/5
- Substrates of CYP3A4/5 with a narrow therapeutic index
- Medications with a known risk for QT prolongation
- Other investigational and antineoplastic therapies
- Herbal preparations/medications and dietary supplements (except for vitamins) including but not limited to: St. John's wort, Kava, ephedra (ma huang), ginkgo biloba, dehydroepiandrosterone (DHEA), yohimbe, saw palmetto, black cohosh and ginseng. Patients should stop using all of these listed herbal medications and dietary supplements prior to first dose of study treatment.

Drugs with QT prolongation

As far as possible, avoid co-administration of QT prolonging drugs or any other drugs with the potential to increase the risk of drug-related QT prolongation (e.g., via a potential DDI that increases the exposure of ribociclib or the exposure of the QT prolonging drug). Please utilize a verified Clinical Drug Information system such as Lexicomp® or UpToDate® for data on drugs with a known risk, possible risk, or conditional risk of QT prolongation and/or Torsades de Pointes (TdP).

Medication with a known risk for QT prolongation are prohibited during study treatment.

Refer to the ribociclib Investigators Brochure and other drug package insert and Appendix B for information on possible interactions with other drugs.

